Visit Window	Day 1	6 to 8 Days After Visit 1	28 to 35 Days After Visit 1	84 to 98 Days After Visit 1	175 to 189 Days After Visit 1	Optimally Within 3 Days After Potential COVID-19 Illness Onset	28 to 35 Days After Potential COVID-19 Illness Visit	
Ask/remind the participant or participant's parent(s)/legal guardian to contact site immediately if participant experiences any symptoms of acute chest pain, shortness of breath, or palpitations	X	X	X*					Refer to Section 8.10.11. *From Cohort 4 onwards, symptoms reported through 6 weeks after study intervention.
Review reactogenicity e-diary data (daily review is optimal during the active diary period)	•	•						If Visit 2 occurs on Day 6, continue to review e-diary data through Day 7.
Review ongoing reactogenicity e-diary symptoms and obtain stop dates		X	X					
Collect AEs and SAEs as appropriate	X	X	X	X	X	X	X	Includes nonserious AEs through Visit 3, any AEs occurring up to 48 hours after a blood draw or nasal swab collection, and SAEs through the end of study (see Section 8.4.1).

								Notes
Visit Identifier	1	2	3	4	5	Unplanned	Unplanned	
Visit Description	Vax 1 Visit	1-Week Follow-Up Visit (Vax 1)	1-Month Follow-Up Visit (Vax 1)	3-Month Follow-Up Visit (Vax 1)	6-Month Follow-Up Visit (Vax 1)	Potential COVID-19 Illness Visit	Potential COVID-19 Convalescent Visit	The COVID-19 illness visit may be conducted as an in-person or telehealth visit. The COVID-19 illness visit is only conducted for symptomatic participants.
Visit Window	Day 1	6 to 8 Days After Visit 1	28 to 35 Days After Visit 1	84 to 98 Days After Visit 1	175 to 189 Days After Visit 1	Optimally Within 3 Days After Potential COVID-19 Illness Onset	28 to 35 Days After Potential COVID-19 Illness Visit	See Section 8.10.7.
Collection of COVID-19/MIS-C-related clinical and laboratory information (including local diagnosis) Assist the participant or participant's parent(s)/legal guardian to delete the e-diary application or collect the provisioned device					X	X	X	

Abbreviations: CRF = case report form; HLA = human leukocyte antigen; IRT = interactive response technology; MIS-C = multisystem inflammatory syndrome in children; NAAT = nucleic acid amplification test; PBMC = peripheral blood mononuclear cell; SARS-CoV-2 = severe acute respiratory syndrome coronavirus 2.

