The investigator or designee must obtain stop dates from the participant or participant's parent(s)/legal guardian for any ongoing local reactions, systemic events, or use of antipyretic medication on the last day that the reactogenicity e-diary was completed. The stop dates should be documented in the source documents and the information entered in the CRF.

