- If the participant is part of the group for description of cell-mediated immune response (select sites only; Cohort 2 and ≥18 years of age only), collect a blood sample (approximately 130 mL) for PBMC isolation.
- Review the participant's reactogenicity e-diary data. Collect stop dates of any reactogenicity e-diary events ongoing on the last day the reactogenicity e-diary was completed and record stop dates in the CRF, if required.
- Remind the participant or participant's parent(s)/legal guardian to contact the site staff or
 investigator if a medically attended event (eg, doctor's visit, emergency room visit) or
 hospitalization occurs.
- From Cohort 4 onwards: Ask the participant or his/her parent(s)/legal guardian to contact the site staff or investigator immediately if the participant experiences acute chest pain, shortness of breath, or palpitations (see Section 8.10.11).
- Ask the participant or participant's parent(s)/legal guardian to contact the site staff or investigator (this could be via the COVID-19 illness e-diary) immediately if the participant experiences any symptoms as detailed in Section 8.10.7.
- Ensure the participant has a self-swab kit in case of COVID-19 symptoms and provide instructions on self-collection of nasal swabs or instruct the participant's parent(s)/legal guardian on the technique for collecting a nasal swab from their child at home.
- Schedule an appointment for the participant to return for the next study visit.
- Complete the source documents.
- The investigator or an authorized designee completes the CRFs.

8.10.4. Visit 4 – 3-Month Follow-Up Visit (84 to 98 Days After Visit 1)

- Perform a clinical assessment. If the clinical assessment indicates that a physical examination is necessary to comprehensively evaluate the participant, perform a physical examination, per Section 8.3.1, and record any findings in the source documents and, if clinically significant, record any findings on the AE CRF.
- Record nonstudy vaccinations as described in Section 6.9.
- Record details of any of the prohibited medications specified in Section 6.9.1 received by the participant if required for his or her clinical care.

- Record AEs as described in Section 8.4.
- Collect a blood sample (approximately 20 mL for participants ≥18 years of age and approximately 10 mL for participants 12 through 17 years of age) for immunogenicity testing, unless advised otherwise by Pfizer.

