	Mild (Grade 1)	Moderate (Grade 2)	Severe (Grade 3)	Potentially Life-Threatening (Grade 4) ^a
Pain at the injection site	Does not interfere with activity	Interferes with activity	Prevents daily activity	Emergency room visit or hospitalization for severe pain
Redness	>2.0 cm to 5.0 cm (5 to 10 measuring device units)	>5.0 cm to 10.0 cm (11 to 20 measuring device units)	>10 cm (≥21 measuring device units)	Necrosis or exfoliative dermatitis
Swelling	>2.0 cm to 5.0 cm (5 to 10 measuring device units)	>5.0 cm to 10.0 cm (11 to 20 measuring device units)	>10 cm (≥21 measuring device units)	Necrosis

Table 4. Local Reaction Grading Scale

If a Grade 3 local reaction is reported in the reactogenicity e-diary, a telephone contact should occur to ascertain further details and determine whether a site visit is clinically indicated. Only an investigator or medically qualified person is able to classify a participant's local reaction as Grade 4. If a participant experiences a confirmed Grade 4 local reaction, the investigator must immediately notify Pfizer.

For each local reaction reported after the study vaccination, the maximum severity grade will be derived for the e-diary collection period (Day 1 through Day 7, where Day 1 is the day of the study vaccination) as follows:

Maximum severity grade = highest grade (maximum severity) within 7 days after administration (Day 1 through Day 7) among severity grades reported for that local reaction.

If a local reaction is captured in more than 1 data source, eg, e-diary, unplanned assessment, and/or the AE CRF, the highest grade (maximum severity) across all sources will be used in the summary.

Duration (First to Last Day Reported)

The duration (days) of each local reaction will be calculated as the number of days from the start of the first reported reaction to the resolution of the last reported reaction, inclusive (last day of reaction – first day of reaction + 1). Resolution is defined as the last day on which the reaction is recorded in the e-diary if the reaction lasts 7 days or less, or the day the reaction ends if it persists beyond the end of the reactogenicity e-diary period following the study vaccination (the latter will be collected on the CRF). If there is no known date when

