a. Only an investigator or medically qualified person is able to classify a reaction as Grade 4; therefore, a confirmed Grade 4 reaction should be reported as an AE in the CRF and assessed by the investigator using the AE intensity grading scale.

the reaction ended, then duration will be missing (unknown). Participants with no reported reaction have no duration.

Onset Day

The onset day of each local reaction will be derived. Onset day is defined as the first day of reporting any severity.

For the onset day of each local reaction, if participants report change in severity of the local reaction, only the first day of reporting that specific local reaction will be counted.

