6.1.1.1.2. Supplemental Analysis

To support the assessment of local reactions, the following endpoints (as defined in Section 3.1.1.1) will be summarized with the same analysis time point and analysis population as above, and appropriate analysis methodology and reporting results:

- Duration (days) of each local reaction after the study vaccination.
- Onset day of each local reaction after the study vaccination.

These continuous endpoints will be summarized by displaying n, mean, median, standard deviation, minimum, and maximum by group.

Figures:

Bar charts with the proportions of participants for each local reaction throughout 7 days after the study vaccination will be plotted by group. The bars will be divided into severity categories to highlight the proportions of participants by maximum severity.

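### Reactions whose end date is still unknown are deleted from the duration tables, which discards a known minimum duration and can lower the reported mean and maximum

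*SAP*

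**What the plan says.** SAP 3.1.1.1 counts duration from the first to the last day of the reaction, inclusive, and has two sources for the end date. Within the diary week, "Resolution is defined as the last day on which the reaction is recorded in the e-diary if the reaction lasts 7 days or less". Otherwise the end is "or the day the reaction ends if it persists beyond the end of the reactogenicity e-diary period following the study vaccination", and "the latter will be collected on the CRF". If neither source gives a date, the rule is "the reaction ended, then duration will be missing (unknown". SAP 3.1.1.2 handles systemic events in a similar way, and SAP 5.3 allows no further imputation of other missing data.

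SAP 6.1.1.1.2 gives the reporting: "These continuous endpoints will be summarized by displaying n, mean, median, standard deviation, minimum, and maximum by group". SAP 6.1.1.2.2 repeats this for systemic events. Neither section has a censored-data method or a lower bound.

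The protocol provides for collecting late end dates. Section 8.3.4 says "The investigator or designee must obtain stop dates" for anything ongoing on the last completed diary day. The Schedule of Activities (1.3) has a row headed "Review ongoing reactogenicity e-diary symptoms and obtain stop dates", marked at two visits. Sections 8.10.2 and 8.10.3 place this at Visits 2 and 3, and at Visit 3 the site must review the diary events still ongoing when the diary was last "completed and record stop dates in the CRF, if required".

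**The concern.** Whether a duration is missing depends on the duration itself. A reaction that starts and stops within the diary week normally has an end date by definition. A reaction that runs past the diary has one only if the site obtains it. The cases that remain unknown are therefore drawn mostly from the reactions that outlast the diary.

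These cases are not uninformative. The diary or a later contact shows that the reaction lasted at least to a given day. Setting the duration to missing discards that minimum and summarises the remainder as if complete. The reported maximum can then only stay the same or fall, and the mean falls if the deleted reactions are longer than average. Tolerability is a primary objective for the Cohort 4 candidates, and with 60 participants per group one deleted reaction can determine the maximum.

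**Working it through.** **Can an unknown end date arise when sites comply?** Visit 1 is Day 1 and Visit 3 is 28 to 35 days later, so Visit 3 falls on Day 29 to Day 36. A reaction with onset on Day 1 to Day 7 that is still ongoing at Visit 3 has lasted at least 29 − 7 + 1 = 23 days and at most 36 − 1 + 1 = 36 days by then. It has no end date when data through Visit 3 are analysed (Protocol 9.4.1, SAP 7.3), so its duration is set to missing. The procedures for Visits 4 and 5 (Protocol 8.10.4 and 8.10.5) list no stop-date step, although the general duty in 8.3.4 is not tied to a visit. Someone who leaves after Visit 2 with an ongoing reaction is lost from the table in the same way.

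**Effect on the mean.** The plan states no figure to reproduce. Define:

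- f = share of reactions that outlast the diary
- u = share of those with no known end date
- m_s, m_l = mean duration of the other reactions and of the outlasting ones

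True mean = (1 − f)·m_s + f·m_l.

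Reported mean = [(1 − f)·m_s + f·(1 − u)·m_l] / (1 − f·u).

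The difference, reported minus true, is −f·u·(m_l − true mean) / (1 − f·u). This is zero when u = 0 and negative whenever m_l exceeds the true mean.

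The documents give none of these inputs, so all are assumed: m_s = 2.5 days, m_l = 10 to 14 days. Worked case with f = 5%, u = 10%, m_l = 10: true mean = 2.375 + 0.5 = 2.875; reported mean = (2.375 + 0.45) / 0.995 = 2.839, which is 1.2% low. With m_l = 14: true 3.075, reported 3.005 / 0.995 = 3.020, which is 1.8% low.

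Percentage by which the mean is too low (m_l = 10 to 14 days):

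| u | f = 1% | f = 5% | f = 10% |
|---|---|---|---|
| 0% | 0 | 0 | 0 |
| 10% | 0.3–0.4 | 1.2–1.8 | 2.1–2.9 |
| 50% | 1.4–2.2 | 6.4–9.1 | 10.9–14.9 |
| 100% | 2.9–4.4 | 13.0–18.7 | 23.1–31.5 |

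**Effect on the maximum and median.** A simulation used 5,000 replicates per setting, with 48 or 240 reactors (80%, assumed, of 60 and of 300), f = 3% or 5%, other reactions lasting 1 to 5 days, and outlasting reactions lasting 8 days or more with a mean of 11. At u = 10% the reported maximum was below the true one in 7.5% to 9.2% of groups, and the average maximum fell by 0.37 to 0.40 day. At u = 50% it was below in 37.5% to 48.0% of groups, and at u = 100% in 77.6% to 100%. The median moved by at most 0.08 day in any setting.

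**Limit of this arithmetic.** It treats every outlasting reaction as long. A reaction that starts on Day 6 and ends on Day 9 outlasts the diary but lasts 4 days. AE-CRF events merged into the summary may also be short and lack a stop date. Both make the figures above lean high.

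**The case against.** A reader might infer that the longest reactions are dropped as a class. The documents do not support that. The SAP gives an outlasting reaction its actual end day from the CRF, the protocol makes obtaining that date mandatory, Protocol 8.3.4.2 has the investigator enter information on persisting local reactions in the CRF, and two visits are scheduled for it. Most reactions of one to three weeks would have ended by Visit 3, so they should have a date and keep their full duration.

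A reader might also take the lower rows of the table as the expected effect. Nothing in the documents suggests that half or all of the stop dates will be missing; those rows only bound the calculation. Nor does the plan include a table of the share of reactions lasting more than 7 days, so there is no such planned statistic to be understated.

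Two further points stand. Because n is shown beside each duration summary and the count with each reaction is reported separately, the number with unknown duration can largely be found by subtraction. And since the median hardly moves, a Kaplan-Meier median adds little to the planned one.

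What remains is narrower. The SAP itself foresees unknown end dates, and a reaction still ongoing at Visit 3 falls under the rule even with perfect site compliance. Subtraction gives the number of such cases but not how long they are known to have lasted.

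**Conclusion.** The concern holds in a limited form and is minor. For reactions still without a stop date after Visits 2 and 3, the rule deletes a known minimum duration, and the resulting error in the mean and maximum is downward if those reactions are longer than average, as they mostly would be. The maximum is the most exposed statistic and the median the least.

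The size depends on a rate of missing stop dates that the documents do not state. If 5% of reactions outlast the diary and 10% of those lack a date, with the assumed mean durations, the mean is about 1% to 2% low. If all dates are obtained, there is no bias.

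It would be wrong to read this as affecting the primary safety results or the trial's hypotheses. The primary reactogenicity percentages and severity summaries do not use duration, and neither do the immunogenicity tests. Duration is a supplemental, descriptive summary.

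**What to change.** - **SAP 3.1.1.1 and 3.1.1.2:** replace the missing-duration rule. Treat an unknown end date as right-censored at the last day the reaction was known to be ongoing, which is the last diary day with the reaction or a later CRF contact.
- **SAP 6.1.1.1.2 and 6.1.1.2.2:** keep the planned descriptive statistics. Report by group the number of reactions censored, and show the maximum as *at least* the stated value where a censored reaction sets it. Add a right-censored (Kaplan-Meier) summary as a supplement.

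This needs only SAP wording and a standard procedure on data already collected. The cost is slightly more complex supplemental tables. No primary endpoint, hypothesis test or sample size changes.

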3.1.1.2. Systemic Events

The systemic events assessed and recorded in the e-diary are fatigue, headache, chills, vomiting, diarrhea, new or worsened muscle pain, and new or worsened joint pain within 7 days after the study vaccination. The e-diary entries from the participant and unplanned clinical assessments within 7 days after vaccination will be the primary data sources for these events. In addition, any events recorded on the AE CRF that are considered systemic events starting within 7 days after vaccination will be consolidated with e-diary data and included in the reactogenicity report. The derivations for systemic events will be handled similar to the way local reactions are handled for presence of event, severity level, duration, and onset day (see Section 3.1.1.1).

The symptoms will be assessed by the participant as absent, mild, moderate, or severe according to the grading scale in Table 5 and recorded in the e-diary. For events recorded in the AE CRF that are considered systemic events and consolidated with e-diary data, the severity will be based on the AE intensity grade recorded in the CRF.

If a Grade 3 systemic event is reported in the reactogenicity e-diary, a telephone contact should occur to ascertain further details and determine whether a site visit is clinically indicated. Only an investigator or medically qualified person is able to classify a participant's systemic event as Grade 4. If a participant experiences a confirmed Grade 4 systemic event, the investigator must immediately notify the sponsor.

Table 5. Systemic Event Grading Scale

	Mild (Grade 1)	Moderate (Grade 2)	Severe (Grade 3)	Potentially Life-Threatening (Grade 4)
Vomiting	1-2 times in 24 hours	>2 times in 24 hours	Requires IV hydration	Emergency room visit or hospitalization for hypotensive shock
Diarrhea	2 to 3 loose stools in 24 hours	4 to 5 loose stools in 24 hours	6 or more loose stools in 24 hours	Emergency room visit or hospitalization for severe diarrhea

Table 5. Systemic Event Grading Scale

	Mild (Grade 1)	Moderate (Grade 2)	Severe (Grade 3)	Potentially Life-Threatening (Grade 4)
Headache	Does not interfere with activity	Some interference with activity	Prevents daily routine activity	Emergency room visit or hospitalization for severe headache
Fatigue/tiredness	Does not interfere with activity	Some interference with activity	Prevents daily routine activity	Emergency room visit or hospitalization for severe fatigue
Chills	Does not interfere with activity	Some interference with activity	Prevents daily routine activity	Emergency room visit or hospitalization for severe chills
New or worsened muscle pain	Does not interfere with activity	Some interference with activity	Prevents daily routine activity	Emergency room visit or hospitalization for severe new or worsened muscle pain
New or worsened joint pain	Does not interfere with activity	Some interference with activity	Prevents daily routine activity	Emergency room visit or hospitalization for severe new or worsened joint pain

Abbreviation: IV = intravenous.

During the 7 days following the study vaccination, potential COVID-19 symptoms that overlap with solicited systemic events (ie, fever, chills, new or increased muscle pain, diarrhea, vomiting) should be assessed by the investigator.

If, in the investigator's opinion, the symptoms are considered more likely to be vaccine reactogenicity, but a participant is required to demonstrate that he or she is SARS-CoV-2-negative, a local SARS-CoV-2 test may be performed: if a positive test result, the symptoms should be recorded in the potential COVID-19 illness CRFs (with potential COVID-19 illness visit completed) rather than as systemic events in the reactogenicity e-diary (refer to the protocol, Sections 8.10.7 and 8.10.8).

Temperature will be collected in the evening, daily, for 7 days following the study vaccination (Days 1 through 7, where Day 1 is the day of the study vaccination) and at any time during the 7 days that fever is suspected. Fever is defined as an oral temperature of $\geq 38.0^{\circ}\text{C}$ ($\geq 100.4^{\circ}\text{F}$). The highest temperature for each day will be recorded in the e-diary.

Temperature will be measured and recorded to 1 decimal place. Temperatures recorded in degrees Fahrenheit will be programmatically converted to degrees Celsius for reporting. Temperatures <35.0°C (<95.0°F) and >42.0°C (>107.6°F) will be excluded from the analysis. Fever will be grouped into ranges for the analysis according to Table 6 below.

If a fever of ≥39.0°C (≥102.1°F) is reported in the reactogenicity e-diary, a telephone contact should occur to ascertain further details and determine whether a site visit is clinically indicated. Only an investigator or medically qualified person is able to confirm a participant's fever as >40.0°C (>104.0°F). If a participant experiences a confirmed fever >40.0°C (>104.0°F), the investigator must immediately notify Pfizer. Fevers >40.0°C (>104.0°F) will be collected as an AE on the CRF and assessed by the investigator using the AE intensity grading scale (Protocol, Section 10.3.3). If a fever is reported in the AE CRF within 7 days after vaccination and no temperature was captured in the CRF, the fever will be included in the reactogenicity summary with "unknown" for temperature range.

Table 6. Scale for Fever

≥38.0-38.4°C (100.4-101.1°F)	
>38.4-38.9°C (101.2-102.0°F)	
>38.9-40.0°C (102.1-104.0°F)	
>40.0°C (>104.0°F)	

If a systemic event is captured in more than 1 data source, eg, e-diary, unplanned assessment, and/or the AE CRF, the highest grade (maximum severity) across all sources will be used in the summary.

3.1.1.3. Antipyretic/Analgesic Medication

The use of antipyretic medication is also recorded in the e-diary from Day 1 through Day 7, where Day 1 is the day of the study vaccination. For the use of antipyretic medication from Day 1 through Day 7 after the study vaccination, the following endpoints and variables will be derived for analysis following the same rules as for local reactions (see Section 3.1.1.1), where applicable.

- Presence (yes or no) of use of antipyretic medication on each day (Day 1 through Day 7)
- Presence (yes or no) of use of antipyretic medication on any day (Day 1 through Day 7)
- Duration (first to last day reported) of use of antipyretic medication
- Onset day of use of antipyretic medication

The use of antipyretic medication will be summarized and included in the systemic event summary tables but will not be considered a systemic event.

3.1.1.4. Adverse Events

AEs will be assessed from the time of informed consent through 1 month after the study vaccination. In addition, any AEs occurring up to 48 hours after any subsequent blood draw must be recorded on the CRF. AEs will be categorized according to MedDRA terms.

Missing AE start dates will be imputed following the Pfizer data standard rules as described in Section 5.3.

The primary safety endpoint "AEs from the study vaccination through 1 month after the study vaccination" and other AE endpoints will be summarized by SOC and PT.

These primary endpoints will be supported by summaries and/or listings of related AEs, severe AEs, immediate AEs (within the first 30 minutes after the study vaccination), and AESIs (defined in Section 8.4.8 of the protocol).

